AURORA HEALTH CARE, INC.

PROTOCOL TITLE: Pilot study for the efficacy and tolerability of Senokot-S[®] in the treatment of diabetic gastroparesis

PRINCIPAL INVESTIGATOR:

[name] Hospitalist [name] [contact] [contact] Email: [contact]

INVESTIGATORS AND KEY PERSONNEL:[name], [name], [name]

This protocol was designed and developed by Aurora Healthcare, Inc. It is intended to be used only in conjunction with institution-specific IRB approval for study entry.

I. Background and Significance

Diabetic gastroparesis can be a difficult-to-treat complication of longstanding diabetes that can significantly compromise quality of life in those affected. Today there is only one medication approved by the FDA for the indication of diabetic gastroparesis and it has received a black box warning due to potential for severe neurological side effects. There are other medications that have found some success in the treatment of diabetic gastroparesis, but they also have the potential for serious side effects, and some are only available through a special use program.¹

II. Specific Aim

The aim of the study is to evaluate the efficacy of the stimulant laxative Senokot-S[®] for the treatment of diabetic gastroparesis. Senokot-S, and its metabolites, are thought to produce peristalsis, drive intra-luminal fluid and electrolyte shifts, and have an irritant effect on the gut mucosa^{2,3}. These complex physiologic mechanisms appear may sufficiently promote stomach emptying, and thereby reduce or eliminate the severity of gastroparesis symptoms. In this open label study, participants will be randomized into high and low dose groups to assess for ideal dosing and tolerability. It is the overall goal of this study to select the most promising dose-strength for the treatment of mild through severe gastroparesis.

(c) Study End Points

- a. Primary Endpoint
 - i. Modified GCSI-DD: Subjects will complete the modified Gastroparesis Cardinal Symptom Index-Daily Diary (mGCSI-DD)^{4,5}. The mGCSI-DD is a validated patient reported outcome (PRO) instrument with excellent testretest reliability, and will be used as the primary instrument to assess for efficacy in this study.

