 - ii. Questions on the mGCSI-DD are a 6-point Likert scale from 0 (none) to very severe (5) that address: nausea, retching, vomiting, stomach fullness, ability to finish a normal-sized meal, feeling excessively full after meals, loss of appetite, bloating, external assessment of stomach size, upper ab-dominal pain or discomfort.
- b. Secondary Endpoint
 - i. Breakthrough medication use: Defined as the change in the frequency of use of breakthrough medication, which is the medication that has been previously prescribed on an as-needed basis to manage symptoms.

Any change in frequency of use of breakthrough medications will be used as a secondary endpoint to assess for efficacy in the study.

 Bowel habits: Subjects will self report bowel habits during the baseline week and through the study period on the same questionnaire form. Since Senokot-S functions primarily as a mild bowel stimulant any significant change in bowel habits will help to assess for tolerability in this study.

IV. Study Design

The Phase II study design will be an open label, pre- and post-treatment assessment, prospective study. Sixty (60) study participants will be recruited over a 5-month period at a single site. Participants will be randomized into two treatment groups, a high- and low-dose, and will take medication dosed orally, twice daily or once daily at night.

V. Experimental Design, Methods, and Study Procedures

- **a.** Initial Identification of Potential Study Subjects Gastroenterologists who have agreed to refer their patient with diabetic gastroparesis for this study will make the initial contact with those patient (study inclusion/exclusion criteria will be provided to these physicians for ready reference). If the patient is interested in participating in the study the gastroenterologists will secure the patient's verbal permission to provide their name and contact information (phone or e-mail) to [name] or another member of the study team. The study team member will contact the patient and arrange a time to meet with them to explain the study and to answer any questions the potential subject may have.

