- b. Screening Visit The screening visit will include reviewing the participants' complete medical history after reviewing and obtaining informed consent. Data from the participant's medical history will be abstracted from the electronic medical record (EMR) and will be securely stored with other study-related data. Participants will be given the mGCSI-DD questionnaire and instructed on its use. At this visit participants will start recording their week of baseline scores by filling out a separate mGCSI-DD questionnaire and Breakthrough Medication Use and Bowel Habits documentation form daily.
- c. Visit 1 will occur 1 week after the screening visit. Participants will return with their mGCSI-DD baseline week of scores. They will be sequentially randomized (1:1) into either the high (8.6/50mg of senna/docusate taken by mouth twice daily) or low (8.6/50mg of senna/docusate taken by mouth once every night) dose study group. To reduce potential subject bias and placebo effect, participants will not be informed as to which dose of study medication they are randomized. They will be given their study medication and their 28-day mGCSI-DD questionnaire sheets, along with a pre-printed return envelope for use after completing their month of treatment in the study. They will be instructed to decrease use of any previously prescribed breakthrough medication as can safely be tolerated. Examples of these medication may include prokinetics such as Reglan (metoclopramide), erythromycin, or domperidone; anti-emtics such as Zofran (ondansetron), or Compazine (prochloperazine); or analgesics such as tramadol,

hydrocodone, or oxycodone. They will also be instructed to resume any breakthrough medication use as previously prescribed at the completion of the study and to continue routine follow ups with their care providers.

Subjects will be instructed to immediately contact the Principal Investigator if they experience episodes of significant diarrhea or rectal bleeding.

Participants may be notified by phone at the end of their study period to verify data or request missing data.

VI. Risks

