Senokot-S side effects. Known side effects of Senokot-S include diarrhea, nausea or vomiting, stomach pain, rectal bleeding, gas, abdominal bloating, and potential for allergic reaction such as skin rash. There have been safety concerns in the past about potential complications from long term use of stimulant laxatives like Senokot-S, such as cathartic colon, increased incidence of colorectal cancer, and liver disease. Several recent studies and reviews refute those previous conclusions and suggest long-term use of mild stimulant laxatives is likely safe when needed^{3,6,7}. Senokot-S is listed as pregnancy category C by the FDA. Women with child bearing potential will be required to use an effective form of birth control while participating in this study.

Ineffective treatment of diabetic gastroparesis. Since this medication has not yet been studied in the treatment of diabetic gastroparesis it is possible that symptoms of the disorder may worsen. The common symptoms of diabetic gastroparesis include nausea, vomiting, postprandial fullness, early satiety, and abdominal pain.

Loss of confidentiality. It is expected that this risk will be low because of numerous safeguards that will be in place, including standard data management procedures with Aurora Health Care.

VII. Benefits

A successful outcome in the proposed study will have immediate implications by reducing the symptoms of diabetic gastroparesis. Such a result will address the significant unmet need by providing a safe, inexpensive pharmacological therapy for a difficult to treat chronic disorder. These findings would allow patients to reduce or eliminate intake of the only FDA-approved therapeutic medication, Reglan[®], which has a black box warning and unfavorable side-effect profile. These known potential benefits are highly likely to outweigh the potential risks of the intervention in this study.

VIII. Study Population

Inclusion Criteria:

- Age 18-75 years, male and non-pregnant, non-lactating females
- Diagnosis of type 1 or type 2 diabetes mellitus
- Clinical diagnosis of diabetic gastroparesis

Exclusion Criteria:

- Diagnosed idiopathic gastroparesis
- A history or inflammatory bowel disease, such as Crohn's disease or ulcerative colitis
- A history of bowel obstruction, current unexplained abdominal pain, or undiagnosed rectal bleeding
- Gastrointestinal cancer
- Any active cancer
- Prior gastric surgery
- End-stage heart disease, liver disease, lung disease

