- Known or suspected drug abuse
- Any condition requiring use of daily narcotics
- Concurrent usage of mineral oil or products containing mineral oil
- Current or recent (within the last 3 months) usage of Senokot-S, docusate or senna

IX. Recruitment and Screening

Recruitment will occur through care provider referrals. Clinicians will be notified of the study through paper advertisement and posters. Initial screening will be done over the phone or through e-mail at the time of referral and will include a medical record review. Final screening and informed consent will be completed during the formal in person screening visit between the participant and research staff and is expected to take about one to two hours.

X. Privacy Plan

Patients will initially be notified of the potential to be in a research study by a current caregiver. If the patient is agreeable to consideration for the study the research team will be contacted by phone or through e-mail by the clinician with the patient's contact information. The patient will then be contacted by a member of the research team via an institution-based phone or EMR e-mail (based on the patient's preference) for initial screening and to set up a clinic visit for final screening and informed consent.

XI. Data Collection

The data to be collected will include a complete medical history of the participant, mGCSI-DD score forms, medication usage and bowel habits forms. Data will not be shared with any outside institutions.

This research study plans to store and manage the subject lists, demographic information, validated questionnaire, study and breakthrough medication use, and bowel habits datasets in REDCap Cloud, a secure electronic data capture application that is based on Vanderbilt University's REDCap application. Flexible for a variety of types of research, REDCap Cloud provides an intuitive data-entry interface for end users into study-specific data collection forms associated with study events. The application includes real time validation rules and query management, audit trails, and the automated export of study data into statistical programs. The REDCap Cloud platform is compliant with GCP predicate rule requirements and US FDA 21 CFR Part 11 pertaining to the use of electronic records and signatures. Aurora Health Care, Inc. has executed an agreement for use of the application with nearly all research studies conducted at Aurora.

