Access to data housed in REDCap Cloud and associated with this research study will be limited to those individuals listed on the IRB approved research study, as well as caregivers from Research Analytics for administrative reasons. Study team members access to the system and the data itself will be limited in accordance with need (i.e., biostatisticians may be limited to simply export the dataset to statistical tools, research coordinators may be limited to entering data, etc.). Overall, limiting access to study team members by need should reduce the risk of accidental disclosure and breach of confidentiality. However, using a cloud-based application may incidentally raise the risk of a breach in confidentiality, and, therefore, Aurora Health Care, Inc. has negotiated strong protections with the vendor in the event of a breach of confidentiality.

XII. Statistical Plan

All category and continuous variables will be described using appropriate descriptive statistics such as frequency, percentage for category variables and mean, standard deviation, median, and range for continuous variables. Pre and post outcomes variables for two groups of patients in the experimental groups will be compared using appropriate parametric and/or non parametric statistical tests. For all statistical tests an alpha level of 0.05 will be used and all statistical analysis will be carried out using SAS version 9.4, SAS Institute, Cary, NC.

XIII. Monitoring Plan

Data monitoring, safety monitoring, and statistical analysis will be done through the research office and principal investigator.

Participants can stop the study at any time for any reason and can resume previous treatments whenever needed. Stopping points will be at the end of the 5 month study period or if a negative trend in mGCSI-DD post-treatment scores is observed.

XIV. Regulatory Requirements

The investigators and all key personnel agree to abide by the determinations of the Aurora IRB, including obtaining documented informed consent prior to inclusion of any individual in this research study. The investigators and all key personnel will comply with reporting requirements as outlined in the Aurora IRB Standard Operating Procedures (SOPs). In addition, investigators will permit access for on-site monitoring by representatives of the Aurora IRB, the Aurora Research Institute Investigator-Initiated Research unit, and the Aurora Research Institute Quality Improvement Program.

XV. References

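### The visible protocol text does not separate stopping Senokot-S from leaving the study, and does not tell an early stopper to keep scoring or to return the diary

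*Combined protocol and SAP*

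**What the plan says.** - **Leaving early.** Section XIII (Monitoring Plan): "Participants can stop the study at any time for any reason and can resume previous treatments whenever needed". This is the only participant-level exit described. Section V.c describes none.
- **Diary return.** At Visit 1 (V.c) participants receive "28-day mGCSI-DD questionnaire sheets, along with a pre-printed return envelope for use after completing their month of treatment in the study". No later visit is described, so the envelope is the only stated route for post-baseline diaries.
- **Adverse effects.** V.c: "Subjects will be instructed to immediately contact the Principal Investigator if they experience episodes of significant diarrhea or rectal bleeding". It does not say what then happens to the tablets or the diary.
- **Recovery of missing data.** V.c: "Participants may be notified by phone at the end of their study period to verify data or request missing data".
- **Tolerability data.** The Study End Points section has bowel habits self-reported at baseline and throughout the study period, on the same form as the questionnaire.
- **Drug-use data.** Section XI plans to hold "study and breakthrough medication use, and bowel habits datasets in REDCap Cloud". It does not mention the date of, or reason for, the last dose.
- **Purpose.** Section II: to "select the most promising dose-strength for the treatment of mild through severe gastroparesis", with both dosing and tolerability in view.
- **Analysis.** Section XII specifies pre/post comparisons at alpha 0.05. It gives no rule for missing diaries or early stoppers.

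**The concern.** Stopping is unlikely to be unrelated to the primary score. Section VI states: "Known side effects of Senokot-S include diarrhea, nausea or vomiting, stomach pain, rectal bleeding, gas, abdominal bloating". The mGCSI-DD items begin with "nausea, retching, vomiting, stomach fullness, ability to finish a normal-sized meal" and go on to bloating and upper abdominal pain. Someone who stops because of nausea, bloating or pain is therefore stopping over symptoms that the primary instrument measures. The high arm takes two tablets a day and the low arm one, so different stopping rates are plausible.

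If those who stop the drug also stop scoring, or keep their sheets because they did not complete treatment, the remaining scores describe mainly those who tolerated their dose. Bowel habits share the form, so tolerability data from the people least able to tolerate the drug are lost too. A rule in the analysis cannot restore a daily rating that was never made. This has to be settled before data collection.

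**Working it through.** The plan has no figure of its own on this point. N = 60 comes without an effect size, SD, power or dropout rate. The check has two parts: reading the text, and an illustration on assumed inputs.

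**Text**

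| Question about a participant who stops the tablets on day 14 | Visible answer |
|---|---|
| Still in the study? | Not stated; XIII speaks only of stopping the study |
| Keep scoring to day 28? | Not stated; 28 days of sheets are already in hand |
| Post the sheets? | Not stated; the envelope is described for treatment completers |
| Will staff ask for them? | Possibly, by an optional call at the end of the period |
| Date of and reason for last dose? | Not specified |

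**Illustration**

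From the documents: 60 participants randomised 1:1, so 30 per arm; 28 diary days; alpha 0.05; items scored 0 to 5. Assumed: a two-sided test; stayers change by -0.8 points in both arms; stoppers are at 0 change once off drug; 2/30 stop in one arm and k/30 in the other, k = 3, 4 or 6; SD of change 0.7 to 1.2; stopping on day 14 where a day is needed.

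*1. End of treatment.* All-randomised arm mean = (30 - k)/30 × (-0.8). This gives -0.747 for k = 2, -0.720 for k = 3, -0.693 for k = 4 and -0.640 for k = 6. Among those still scoring, the arms differ by 0 in every case.

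SE of the difference = SD × √(2/30): 0.181 at SD 0.7 and 0.310 at SD 1.2. The probability that the arm with less stopping shows the better mean is Φ(difference/SE).

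| Stopping | All-randomised difference | Pick probability, SD 1.2 to 0.7 | Still scoring only |
|---|---|---|---|
| 3/30 v 2/30 | 0.027 | 53% to 56% | 50% |
| 4/30 v 2/30 | 0.053 | 57% to 62% | 50% |
| 6/30 v 2/30 | 0.107 | 63% to 72% | 50% |

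Even in the widest case the difference is only 0.34 to 0.59 SE. Two-sided t-test power on 58 df is 6% to 9%.

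*2. Mean over diary days, 6/30 v 2/30, sheets scored before stopping are returned.* Let a be a stopper's change while on drug and d the stopping day. A stopper contributes a if only available days count, and a × d/28 if scoring continues to day 28 at 0 change. The difference hidden by the loss is -a × (1 - d/28) × 4/30. At d = 14:

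- a = -0.8: 0.8 × 0.5 × 4/30 = 0.053 hidden.
- a = 0: nothing hidden.
- a = +0.4: -0.027, so the loss exaggerates the difference (0.160 on available days against 0.133 with full scoring).

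The direction therefore depends on how stoppers fared on drug. With equal stopping the proportion term is 0 and so is the bias.

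*3. As 2, but stoppers' sheets are never posted.* Those who return sheets show 0 difference. The all-randomised 28-day difference is 4/30 × (0.8 + a × 14/28), which is 0.053, 0.107 or 0.133 for a = -0.8, 0 or +0.4.

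*4. Diary days lost.* Each arm has 30 × 28 = 840 diary days. Three stoppers at day 14 lose 42 (5%); six lose 84 (10%).

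**The case against.** The strongest reply is that the text is less silent than it looks. Participants get all 28 days of sheets at Visit 1 and are instructed on the questionnaire at screening. Bowel habits are to be reported throughout the study period, not only until the last dose. The envelope wording describes the expected course and does not forbid earlier return, and staff may telephone for missing data. Consent pages, the diary form and any participant instruction sheet cannot be seen and may cover the point. All of this stands, and it limits the claim to the visible text. It does not remove the gap: the study period is undefined for someone who has stopped the drug, the call is optional, and a call cannot recreate unscored days.

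A second reply is that on-treatment symptoms plus stopping rates are a defensible target for a 28-day open-label dose-selection pilot, and that off-drug days and resumed treatment dilute an all-randomised comparison. That also stands. Which comparison leads is a choice of estimand. Complete diaries allow both; under the present text, post-stop scores would exist only for those who happened to continue.

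A reader might infer more than the documents support:

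- That early stoppers' data will be lost. Some may carry on scoring and return their sheets.
- That the wrong dose would probably be chosen. The documents give no stopping rates, effects or SD. The 63% to 72% figure belongs only to the widest assumed imbalance, and all the pick probabilities assume choice on mean score alone. Section II also names tolerability, and a threefold difference in stopping, if recorded, would be seen directly.

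**Conclusion.** The concern holds in limited form. The visible protocol leaves the handling of an early stopper's diary undefined at the point where primary and tolerability data are most likely to be lost selectively. Bias requires that stoppers also stop scoring or do not return sheets, and that stopping differs by arm. Neither can be established from the documents.

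On the assumed inputs the all-randomised end-of-treatment difference that goes unseen is 0.03 to 0.11 points on a 0 to 5 scale. Significance tests would seldom change. A choice made on the better mean would be affected more: about 53% to 72% against 50% across the stopping range shown. The direction can reverse, and with equal stopping the effect is nil. The change is worth making because it costs little and unscored days cannot be recovered later.

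**What to change.** 1. In V.c and XIII, separate stopping study medication from withdrawing consent.
2. Ask those who stop the drug but do not withdraw to complete the same daily sheets to day 28, and to post all sheets whether or not treatment was completed.
3. Record the date of and reason for the last dose in the study-medication-use data already planned in XI.
4. In XII, report stopping rates by arm, with both an all-randomised comparison (available scores) and an on-treatment comparison, and say in advance which leads.

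The cost is a few sentences of protocol text, a line of participant instruction and one date-and-reason entry. No visit is added, and participants already hold the sheets and envelope. The downsides are a small burden on those who stop, and some dilution of the all-randomised comparison by off-drug days or resumed treatment, which XIII permits. It does not help for participants who withdraw fully. If the consent form or instruction sheet already says this, the protocol need only be brought into line.

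### Does ending the study at 5 months cut off the last participants, given that recruitment also takes 5 months?

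*Combined protocol and SAP*

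**What the plan says.** Section IV (Study Design) sets the size and the recruitment window: "Sixty (60) study participants will be recruited over a 5-month period at a single site".

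Section V sets the time each participant needs. After screening comes a baseline week: "Visit 1 will occur 1 week after the screening visit". At Visit 1 participants are allocated 1:1 to the two dose groups and "They will be given their study medication and their 28-day mGCSI-DD questionnaire sheets". They also receive a "pre-printed return envelope for use after completing their month of treatment in the study". A data query may follow: "Participants may be notified by phone at the end of their study period to verify data or request missing data".

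Section XIII (Monitoring Plan) then gives the calendar stop, "Stopping points will be at the end of the 5 month study period", next to a second stop based on the trend in symptom scores. It does not say whether the calendar stop closes enrolment or ends data collection. No section mentions participants who are still in baseline or on treatment at that date.

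Section XII (Statistical Plan) says of the analysis: "Pre and post outcomes variables for two groups of patients in the experimental groups will be compared". It does not say which of the 28 days count as the post-treatment value.

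**The concern.** One length of time, 5 months, seems to serve both as the recruitment window and as the length of the whole study, with nothing added for follow-up. If participants may be screened up to the last day and data collection also ends that day, anyone screened in the final 35 days cannot return a full 28-day diary. That diary carries the primary endpoint. The shortfall would be set by the calendar, and someone would have to decide afterwards how to use partial diaries. Two teams following the same text could deliver different data sets: about 46 complete diaries or 60, before any dropout.

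**Working it through.** The documents give no count of incomplete participants and no derivation of the sample size, so there is no figure of the plan's own to reproduce. The check is accrual arithmetic under each reading.

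**Inputs**
- N = 60 recruited over 5 months (Section IV).
- Baseline of 7 days and diary of 28 days (Section V), so 7 + 28 = 35 days from screening.
- T = 152 days for 5 months. This is an assumption; 150 to 153 days are possible.
- Accrual pattern: not given. Even accrual is assumed first and then varied.

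**Reading A: data collection ends at month 5**
- Even accrual dated at screening: 60 × 35/152 = 13.8 incomplete (14.0 with T = 150, 13.7 with T = 153). Complete: 60 − 13.8 = 46.2.
- Of the 13.8, those screened in the last week are not yet randomised: 60 × 7/152 = 2.8. The other 60 × 28/152 = 11.1 have part of a treatment diary, 14 days on average.
- Treatment diary-days lost: 2.76 × 28 + 11.05 × 14 = 232 of 60 × 28 = 1,680, or 14%.
- If the 60 are counted as recruited at Visit 1 instead, the window is 28 days: 60 × 28/152 = 11.1 incomplete.
- Accrual rising linearly from zero: 60 × [1 − (117/152)²] = 24.5.
- Accrual falling linearly to zero: 60 × (35/152)² = 3.2.
- If the 60th participant is screened by day 152 − 35 = 117, nobody is incomplete even on this reading.

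The range of about 3 to 24 illustrates the dependence on accrual. It is not a bound.

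**Reading B: enrolment closes at month 5**
- Incomplete because of the calendar: 0.
- A participant screened on the last day finishes on day 152 + 35 = 187, which is 187/30.4 = 6.2 months, plus time for mail return and queries.

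**Which reading the text supports**
- The only other 5-month period in the document is the recruitment window in Section IV, so that is a natural referent for the phrase in Section XIII.
- Section V ties the return of the diary to completion of each participant's own month and places the phone call at the end of that participant's own study period. Neither is tied to a common calendar date.
- No section says that anyone is withdrawn on a calendar date.

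**Effect on the comparison of doses**
- Allocation is described as follows: "They will be sequentially randomized (1:1) into either the high" or the low dose group. A calendar cut-off would be expected to fall about equally on both arms, 13.8/2 = 6.9 per arm under even accrual. It gives no reason to expect one dose to be favoured.

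**The case for a change.** The strongest case for a change is that Reading A is not strained. Elsewhere the protocol uses the term study period for data collection: bowel habits are recorded from the baseline week through it. In Section XIII the calendar stop sits beside a stop for worsening scores and follows a sentence about participants leaving the study, and closing enrolment is not mentioned. A coordinator has to supply the enrolment reading. A literal stop would leave partial diaries for the primary endpoint, and a within-group comparison of before and after could then lean on early treatment days. One sentence would remove the doubt at almost no cost.

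Part of this stands. The sentence is ambiguous, and the arithmetic under the literal reading is right. Three things limit its weight. First, the loss depends on the literal reading combined with enrolment running into the last 35 days, and no section requires enrolment to run that late. Second, the undefined post-treatment window in Section XII is a separate gap that exists whatever month 5 means. Third, the documents give nothing from which to size a shift in the within-group comparison, and no precision target against which a loss could be judged.

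**Conclusion.** The concern is a minor ambiguity in wording and does not call for a change to the plan. If the calendar stop closes enrolment, which the text supports at least as well, the loss is 0 of 60 and the study runs up to about 6.2 months. If it ends data collection, about 14 of 60 would lack a complete diary. That figure assumes 152 days, even accrual and dating at screening; it is about 11 if dated at Visit 1, and illustratively about 3 to 24 under uneven accrual. Dropout is left out because the documents give no rate.

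No bias between the arms, missed power figure or wrong conclusion follows from the text as it stands. What is missing is an operational detail that the study team at a single site can be expected to settle sensibly, and settling it may be a matter of wording only.

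### Does the stop for a negative trend in symptom scores (Section XIII) need a fuller definition before the trial can rely on it?

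*Combined protocol and SAP*

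**What the plan says.** Section XIII has one sentence on ending the study. It ends with the five-month study period, or earlier "if a negative trend in mGCSI-DD post-treatment scores is observed". A separate sentence just before it lets individual participants leave whenever they wish and return to their earlier treatment. Monitoring and analysis rest with the research office and the principal investigator.

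Other sections supply the context:

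- **Scale.** The Study End Points section scores each mGCSI-DD item from 0 (none) to 5 (very severe), so a higher score is worse.
- **Baseline.** Diaries are kept for a week before treatment. At Visit 1 (Section V.c), "Participants will return with their mGCSI-DD baseline week of scores".
- **Return of diaries.** The 28-day sheets are handed out "along with a pre-printed return envelope for use after completing their month of treatment in the study".
- **Breakthrough medication.** Also at Visit 1: "They will be instructed to decrease use of any previously prescribed breakthrough medication as can safely be tolerated".
- **Size and pace.** Section IV: "Sixty (60) study participants will be recruited over a 5-month period at a single site".
- **Analysis.** Section XII compares pre and post outcomes at an alpha of 0.05. It describes no interim analysis and does not tie that alpha to stopping.

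**The concern.** This is the only data-driven stop in the protocol, and taken alone it leaves much open. On a scale where a fall is improvement, a negative trend read numerically would stop the trial for benefit. The clause mentions post-treatment scores without saying what they are compared with. It does not say how large a trend must be, when scores are examined, or whether one dose arm can stop the study. Because participants are asked to cut back breakthrough medication, a rise in scores might reflect that instruction rather than the study drug, and no untreated arm is available to separate the two.

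If these matters are settled only after scores have been seen, in an open-label trial whose monitors also analyse the data, the trial could stop on noise. It could also continue when one arm is getting worse.

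**Working it through.** The plan states no threshold, look schedule, SD or power for this rule, so there is no figure to reproduce. The check is first textual, then an illustration on stated assumptions.

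**What the text settles**

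- *Direction.* Section VI warns that "it is possible that symptoms of the disorder may worsen". Section VII says: "A successful outcome in the proposed study will have immediate implications by reducing the symptoms of diabetic gastroparesis". Worsening is the harm and a fall in symptoms is the success, so negative means unfavourable.
- *Level.* The clause is paired with the end of a five-month period. One participant contributes 7 + 28 = 35 days, so that pairing can only describe the trial. Individual withdrawal has its own sentence.
- *Comparator.* Section IV calls the design a pre- and post-treatment assessment, Section XII compares pre with post, and a baseline week is collected for that purpose. Change from baseline is the natural reading.

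**What the text leaves open:** the criterion for a trend, the look times, and per arm or pooled.

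**How much the open items could matter.** Assume independent post-minus-baseline changes in SD units, normal with mean μ (negative is improvement) and SD 1. Assume a stop if the mean change exceeds 0 at one look. Then P(stop) = Φ(μ√n). If either arm can trigger, P = 1 − (1 − p)², with p taken at n = 15.

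| True change | Pooled, n = 30 | Either arm, 15 each |
|---|---|---|
| none | Φ(0) = 0.500 | 1 − 0.5² = 0.750 |
| 0.3 SD better | Φ(−1.64) = 0.050 | 0.230 |
| 0.5 SD better | Φ(−2.74) = 0.003 | 0.052 |

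With k equally spaced looks and no true change, the pooled chance is 1 − C(2k,k)/4^k. For k = 2 it is 1 − 6/16 = 0.625, and for k = 5 it is 1 − 252/1024 = 0.754. If either arm can trigger, these become 1 − 0.375² = 0.859 and 1 − 0.246² = 0.939. If instead each look needed a one-sided 0.025 result, the pooled chance would be about 2.5% at one look and, by simulation, about 7% over five. The answer is set almost wholly by the trigger one assumes.

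**What each way of fixing it would cost**

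- *Chance allowance.* With a one-sided 95% bound, detection of a 0.5 SD worsening at n = 30 falls from Φ(2.74) = 0.997 to Φ(2.74 − 1.645) = 0.863 (0.848 by noncentral t). At n = 15 it falls from Φ(1.94) = 0.974 to Φ(1.94 − 1.645) = 0.615 (0.578 by noncentral t).
- *Pooling.* If one arm worsens by 0.5 SD and the other improves by 0.5 SD, the pooled mean is 0 and an any-worsening rule stops 50% of the time. The worsening arm alone would trigger 97% of the time. At 0.3 SD worse and 0.5 SD better, the pooled mean is −0.1, giving Φ(−0.55) = 0.29 against Φ(1.16) = 0.88.
- *Per arm.* This restores sensitivity but raises the null stop chance from 50% to 75% under the any-worsening trigger.

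**How many looks are practical.** Assume even accrual of 60/5 = 12 a month. Follow-up is 35/30.44 = 1.15 months, so 30 completers are reached at 30/12 + 1.15 = month 3.65, with 12 × 3.65 = 43.8 enrolled. By month 5 there are 12 × (5 − 1.15) = 46.2 completers. With an assumed 14-day postal lag (49/30.44 = 1.61 months), these become month 4.1 for 30 returned diaries and 12 × (5 − 1.61) = 40.7 diaries by month 5. Most enrolment is over before a meaningful trend can be seen.

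**The case for a change.** The strongest case for a change is that the same people monitor and analyse an open-label trial, and a few words would prevent choices made after seeing the scores. With two arms and an aim of selecting a dose, arm or pooled matters, as the 50% against 97% comparison shows. The missing criterion is the largest gap, since the assumed trigger alone can move the null stop chance from about 2.5% to about 94%.

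The gaps are real, but that does not make the plan wrong. Asking the sponsor to state the arm and the look times, without a reason to prefer any option, asks for detail and corrects no error. Writing in any increase from baseline would adopt the very trigger that fires half the time by chance. Adding a bound would make a protective stop slower. A cautious stop by judgement is a legitimate choice in a pilot of this size.

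The breakthrough-medication point stands only as a caution in reading a rise. Its size is unknown, and reduction is limited to what participants tolerate. An open-label placebo response would push scores the other way. Breakthrough use is recorded daily from the baseline week and is a secondary endpoint, so the monitors already hold what they need to read a rise in context. For a protective stop, worsening under the regimen as given may matter whatever its cause.

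**Conclusion.** No change follows. Direction, trial level and a baseline comparator can be read from the protocol as a whole, and calling worsening a negative trend is loose wording only. The criterion, look times and arm or pooled are left open. This is a gap that those monitoring the trial can fill sensibly, and each option trades false stops against missed harm.

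The consequence is limited. The stop can only end the study for worsening, so it gives no extra chance to claim improvement from baseline. Participants can leave at any time without it. Mailed diaries mean about 44 of 60 are already enrolled when 30 have completed, even with no postal delay. If the drug improves scores by 0.5 SD, one pooled look stops the trial wrongly about 0.3% of the time even under the most sensitive trigger considered; if either arm could trigger, about 5%.

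The stop probabilities rest on independent normal changes and on a trigger the plan does not state, and the timing rests on even accrual. They show that the choice of trigger matters, not that the plan has chosen badly. A clarifying phrase at some later amendment would do no harm, but neither the conduct nor the analysis of the trial depends on it.
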